3 STUDY DESIGN

This is an evaluation of an ongoing national screening programme. In years 1 and 2, we will implement an enhanced metrics and evaluation project at selected sites in all provinces across South Africa to measure 6-month outcomes of this programme, along with operational challenges. In years 2 to 5 we will implement programmatic strategies to maximize 6-month cryptococcal meningitis-free survival.

Per South African standard of care, those with a CD4<100 cells/µL will reflexively get a CRAG test performed on remaining blood specimen. We expect the majority of these persons to be asymptomatic outpatients presenting for routine HIV care, though a small proportion will be persons who present to care because they feel unwell. All participants will receive standard of care treatment for asymptomatic cryptococcal antigenaemia, per South African HIV guidelines.

Primary Objective (years 1 and 2): To implement enhanced surveillance at selected sites to determine the outcomes (overall and for pre-specified subgroups) of a national reflex laboratory CRAG screening and pre-emptive treatment programme in South Africa. We estimate performing enhanced surveillance at **approximately 400 clinics out of 4500 clinics nationally**. A list of surveillance facilities will be agreed upon in discussion with provincial departments of health.

We will assess the cascade of care from CD4 testing to CRAG testing, to receipt of CRAG results by healthcare provider, assessment for symptoms, lumbar puncture if indicated, preemptive treatment for those asymptomatic, and 6-month outcomes.

The initial surveillance performed in Objective 1 will establish **baseline 6-month CRAG+ outcomes** (Year 1 and 2) from which subsequent programmatic interventions will seek to improve.

Subgroup Analyses

A number of subgroup analyses will be performed to understand optimal CRAG screening and treatment programmes. For example, we will compare outcomes amongst CRAG+ persons who:

- a) initiated on ART before CD4/ CRAG results are known (same-day ART initiation in the context of universal HIV test-and-treat) to those who have ART delayed until a minimum of 2 weeks of antifungal treatment completion
- b) rural clinics vs. urban centres
- c) high titres (\geq 160) vs. low titres (<160)

- d) clinics that routinely perform lumbar punctures to those that are unable to perform lumbar punctures (stratified by titre)

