 - o Subset of those with cryptococcal meningitis

Primary objective (Years 2-5): To implement and test programmatic interventions to improve 6-month cryptococcal-free survival.

Starting in Year 2, we will use the data generated from the preceding years regarding the barriers in the cascade-of-care to identify areas which may require programmatic interventions to improve 6-month CRAG+ outcomes. Such interventions will be implemented at selected enhanced surveillance facilities to determine their effectiveness (pre/post intervention) as well as compared with facilities without the intervention. The exact intervention(s) to be implemented will be dependent on the challenges observed during the initial surveillance. Examples may include:

Intervention 1: Stratification by CRAG titre

For a subset of CRAG+ persons in the enhanced surveillance cohort, we will perform CRAG titres. We anticipate performing these retrospectively (batched) initially, and then for a short time prospectively to evaluate whether this is feasible in the lab. CRAG titres will not be reported to treating clinicians initially. Once data have been collected in years 1 and 2 regarding outcomes of those with high CRAG titres vs. low CRAG titres, we may then routinely report CRAG titre results with CD4 results. An information sheet may be attached to the lab results educating healthcare workers of the CRAG+ result and suggestions for management. Alternatively, this

information will be included in routine healthcare worker training materials. We may recommend that those with a CRAG titre \geq 160 have a LP performed to evaluate for meningitis, given that these persons are at high risk for meningitis and death. The outcome will be 6-month survival.

We hypothesize those with CRAG titres \geq 160 will benefit from recommended lumbar punctures to detect occult meningitis (defined as CSF CRAG+ and/or culture-positive) in comparison with those who decline LPs. Conversely, we hypothesize those with low CRAG titres <160, do not have a survival benefit when receiving LPs (i.e. due to low prevalence of asymptomatic occult meningitis).

Intervention 2: Healthcare provider training

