8.1 Statistical Analysis Plan

The rate (with 95% confidence interval) for the primary and secondary events will be estimated overall and for pre-specified subgroups during the first 2 years of the study. Those rates will subsequently be compared with the rates after programmatic changes have been made (during years 2-5) to increase the effectiveness of the national screening program.

For the subgroups we will also use time-to-event methods to compare the primary and selected secondary endpoints. The table below reports detectable hazard ratios for the primary event with 80% and 90% power, assuming a two-sided alpha=0.05, 70% CM-free survival in the control group, and the stated number of subgroup participants. For example, if CSF CRAG titre data are available for 1200 participants (with 300 having a titre \geq 160), then we can detect a hazard ratio as small as 1.37, for an almost 10% difference in event-free survival.

Detectable Hazard Ratios for Subgroups					
(Assuming two-sided α =0.05 and 70% event-free survival in the control group)					
		80% Power		90% Power	
	N per		Proportion		Proportion
Subgroup	group	HR	Surviving	HR	Surviving
High CSF CRAG titre	300	1.37	0.61	1.44	0.60
(≥1:160)					
Control	900				
(CSF CRAG titre < 1:160)					

The a priori subgroups of interest are:

- High CRAG titres (\geq 1:160) vs. low titres (<1:160)
- Male vs. Female
- Pregnant vs. Non-pregnant
- Liver Disease (ALT>3x Upper Limit of Normal) vs. No liver disease

- Geographic Location (urban vs. rural)
- Timing of ART Initiation
 - On pre-existing ART
 - Initiated on ART before CD4/ CRAG results are known (same-day ART initiation in the context of universal HIV test-and-treat)
 - ART initiated at 2 weeks
 - ART initiated at >=4 weeks
- Clinic-level outcomes (i.e. cluster) based on proportion of CRAG+ persons receiving Lumbar Punctures.
- Duration of fluconazole use
- Fluconazole secondary prophylaxis vs. none

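### The LP hypotheses are framed by who receives or declines LP although the intervention is a recommendation; the facility and pre/post comparison already planned should be their test

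*Protocol*

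**What the plan says.** Section 3, Intervention 1, measures CRAG titres in a subset of CRAG-positive patients. They are batched retrospectively at first and not reported to clinicians. Later the titre may be reported and an LP recommended at ≥160. On the outcome it says: "The outcome will be 6-month survival".

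Two hypotheses follow. Patients with titres ≥160 "will benefit from recommended lumbar punctures to detect occult meningitis (defined as CSF CRAG+ and/or culture-positive) in comparison with those who decline LPs". Patients with titres below 160 "do not have a survival benefit when receiving LPs", which the protocol attributes to a low prevalence of occult meningitis.

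Earlier in the same section, interventions in general are to be run at selected facilities "to determine their effectiveness (pre/post intervention) as well as compared with facilities without the intervention".

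Two further contrasts use clinic LP practice. Subgroup (d) in section 3 compares clinics that routinely do LPs with clinics that cannot, stratified by titre. Section 8.1 lists "Clinic-level outcomes (i.e. cluster) based on proportion of CRAG+ persons receiving Lumbar Punctures". Section 2.2 applies 6-month meningitis-free survival to the subgroups. Section 8 counts any death and symptomatic meningitis as failures.

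On who gets an LP, section 1.1 (knowledge gap 6) says that the procedure is very poorly accepted. The cascade of care in section 1.1 and the data-collection text in section 3 link LP to symptoms.

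**The concern.** What a facility can adopt is the recommendation. The stated contrasts ask a different question: whether patients who had the procedure fared better than patients who refused it or did not have it. Where few accept, acceptors are a self-selected group and may differ from decliners in illness, distance from care or engagement.

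Below 160 no recommendation is foreseen, so LPs there would mostly follow symptoms. Recipients would then tend to be sicker, which could hide a benefit and resemble the hypothesised absence of one.

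The clinic-level contrasts raise a smaller, separate problem. A symptomatic, non-fatal meningitis is less likely to be confirmed where LP cannot be done, so the meningitis part of the endpoint may be recorded unevenly. At stake is whether the study can say anything reliable about an LP recommendation guided by titre.

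**Working it through.** **Yardstick.** No LP contrast is sized, so the only figure for scale is the section 8.1 titre subgroup: 300 versus 900, 70% event-free survival in controls, two-sided alpha 0.05.
- HR 1.37: 0.70^1.37 = 0.613 (stated 0.61). A two-proportion calculation gives power 0.787.
- HR 1.44: 0.70^1.44 = 0.598 (stated 0.60). Power is 0.896.
- Event-based formulas bracket these: Schoenfeld 1.39 and 1.46, Freedman 1.36 and 1.42.

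The stated figures reproduce. The inverse of 1.37 is 1/1.37 = 0.73.

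**Selection, true LP effect zero.** All inputs here are assumptions: base 6-month death risk b = 0.20 or 0.30, and a frailty factor with risk ratio RR = 1.5 to 3 and prevalence p in each group.
- Group risk = b × (1 + p × (RR − 1)).
- Apparent HR, accepted versus declined = ln(1 − risk accepted) / ln(1 − risk declined).
- The last column is the chance of p < 0.05 with 150 versus 150, an assumed even split of the 300.

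| b | RR | p accepted / declined | Risk accepted / declined | HR | P(p < 0.05) |
|---|---|---|---|---|---|
| 0.20 | 1.5 | 0.20 / 0.30 | 0.22 / 0.23 | 0.95 | 0.05 |
| 0.20 | 2 | 0.20 / 0.40 | 0.24 / 0.28 | 0.84 | 0.12 |
| 0.20 | 3 | 0.20 / 0.40 | 0.28 / 0.36 | 0.74 | 0.32 |
| 0.30 | 3 | 0.20 / 0.40 | 0.42 / 0.54 | 0.70 | 0.55 |
| 0.20 | 1.5 | 0.40 / 0.20 | 0.24 / 0.22 | 1.10 | 0.07 |
| 0.20 | 3 | 0.40 / 0.20 | 0.36 / 0.28 | 1.36 | 0.32 |
| 0.30 | 3 | 0.40 / 0.20 | 0.54 / 0.42 | 1.43 | 0.55 |

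The b = 0.30, RR = 3 rows are pessimistic. Their death risks of 42% and 54% exceed the 39% event risk (1 − 0.61) that section 8.1 implies for high titres. The b = 0.20 rows stay below 39% and still reach 0.74 and 1.36.

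**Indication, titre <160.** Suppose recipients are sicker: p 0.40 versus 0.20, b = 0.20, RR = 2. The risks are 0.28 and 0.24, so HR = ln(0.72)/ln(0.76) = 1.20. To a first approximation a true LP hazard ratio of 0.83 would then appear as 0.83 × 1.20 = 1.00.

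**Clinic-level contrasts on meningitis-free survival.** Assume 30% true events in both kinds of clinic, of which 10 to 15 points are non-fatal symptomatic meningitis. Assume full capture at LP clinics and 50% to 75% at clinics without LP. Gap = non-fatal meningitis × (1 − capture).
- Low end: 0.10 × 0.25 = 2.5 points; HR = ln(0.700)/ln(0.725) = 1.11.
- High end: 0.15 × 0.50 = 7.5 points; HR = ln(0.700)/ln(0.775) = 1.40.

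LP clinics look worse with no true difference. With equal capture, or with all-cause death as the outcome, the HR is 1.00.

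**Dilution under a comparison by recommendation.** Observed difference = rise in LP uptake × effect in those whose LP status changes. For a 9-point effect (0.70 − 0.61) and an assumed rise of 20, 40 or 60 points, the observed difference is 1.8, 3.6 or 5.4 points.

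**The case against.** The strongest reply is that section 3 already plans pre/post and between-facility evaluation, and that this governs Intervention 1. That stands: the decliner contrast is not the only comparison available. But it is the only comparator named in the LP hypothesis, and the protocol does not say which prevails. Confounder adjustment may sit in an analysis plan that is not shown. It could reduce the bias but would not change the question the protocol asks.

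Several stronger readings are tempting and fail on the text:
- **Acceptors have a survival advantage because they had to return alive and be reached.** Decliners also had to be alive and reached to be offered the procedure.
- **More LPs inflate failures by finding occult meningitis.** Section 1.1 does report 2 of 12 patients without neurologic symptoms with meningitis in CSF. Section 8 counts only symptomatic meningitis, so such cases add nothing to failures as written.
- **Survival is the wrong or an inconsistent outcome for Intervention 1.** LP detection cannot affect it, which makes it suitable here.
- **A non-significant low-titre result will be read as proof of no benefit.** The protocol states a hypothesis, not that inference rule.

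Uneven capture between clinics is partly offset by chart review, by GERMS surveillance and by counting every death. The explanation given for the low-titre hypothesis concerns asymptomatic disease, but the contrast is not restricted to asymptomatic patients. Intervention 1 is also conditional, and nothing says that this contrast alone decides national policy.

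**Conclusion.** The point holds in a limited form. The LP hypotheses are stated by receipt or refusal for an intervention that is a recommendation, and that exposes them to confounding by choice and by indication. Neither direction nor size can be known from the protocol. Under the assumed imbalances the apparent hazard ratio under no effect runs from 0.70 to 1.43. It comes near the section 8.1 yardstick only when the frailty factor is strong and unevenly spread; milder imbalances give 0.84 to 0.95 or about 1.10. That yardstick belongs to the titre comparison on meningitis-free survival, so it indicates scale only.

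A reader might infer that the LP estimate is certain to be wrong, or wrong in a known direction. The documents support only a serious risk. The clinic-level issue is secondary: 2.5 to 7.5 points, depending wholly on the assumed share of non-fatal meningitis and on capture.

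**What to change.** - In Intervention 1, make the evaluation already planned the test of the LP hypothesis. Compare all patients with titre ≥160 at facilities or in periods with the recommendation against those without it, by recommendation and not by receipt, on 6-month survival. Batched, unreported titres identify the comparison patients.
- For titre <160, report the effect estimate, its confidence interval and the titre interaction.
- Keep accepted versus declined as a description of uptake and outcomes.
- For subgroup (d) and the section 8.1 clinic LP subgroup, report all-cause 6-month survival beside meningitis-free survival. State that the section 8 definition applies, so asymptomatic meningitis found by LP is not a failure.

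The change is mainly wording. Titres are planned for a subset only, so they must also be batched at comparison facilities; section 9.4 already allows batched titre testing. The main loss is dilution by non-uptake. The comparison also remains non-randomised, so time trends and facility differences still need handling, and it estimates the reported titre and recommendation as a package.

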3.1 Exploratory studies

We will evaluate the impact of CRAG screening programs on the timing of ART initiation, particularly in the context of a same-day HIV test-and-treat strategy. We plan to perform a casecontrol study, of 2 CRAG negative persons for each CRAG positive person, matched by clinic, CD4 count, and CD4 date, and will evaluate time to ART initiation from CD4 testing. This casecontrol study will be conducted at a small subset of facilities in each province. Data for the casecontrol study will be collected retrospectively, as specified on page 29.

Additionally we will describe the prevalence of opportunistic infections amongst CRAG+ and CRAG negative persons. Opportunistic infections of particular interest include tuberculosis, toxoplasmosis, other fungal infections. These data will be obtained from laboratory records: toxoplasmosis serology, MTB/Rif GeneXpert results, beta d glucan results, urine LAM, etc.

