The National Health Laboratory Service (NHLS) is a single parastatal entity comprising of a large integrated national network of diagnostic pathology laboratories that provide clinical services to government hospitals and clinics. This captures >90% of HIV care delivery in South Africa. Lab tests, including CD4 and CRAG, are archived in the NHLS Corporate Data Warehouse (CDW). Relevant identifying information (contained on the original specimen request form) accompany these records, e.g. medical record (hospital/ facility) number, age, sex, NHLS lab testing site, and clinic site. The CDW servers are located at the NHLS in Sandringham, Johannesburg, where the NICD is co-located on the NHLS campus (**Figure**). This system has been used for monitoring HIV viral load testing, CD4 count testing, GeneXpert MTB testing and for the prevention of mother-to-child transmission (PMTCT) therapy to generate aggregate and granular performance data, down to the individual site level. In 2013, 362,000 CD4 counts <100 cells/µL were resulted in the NHLS CDW of which approximately

80% came from unique individuals. The proportion of CD4<100 cells/ μ L in 2013 was ~10% of 3.8 million CD4 counts run by the NHLS in South Africa, representing a sizeable population. Other routine laboratory results are also available through the CDW, which can potentially be used as a proxy for retention-in-care.

With national implementation of CRAG screening, data from the NHLS CDW will be used to: 1) determine CRAG+ prevalence by NHLS CD4 lab, province, district, sub-district and clinic level; 2) determine the number eligible for CRAG screening and the number who are CRAG screened (i.e. screening coverage). Within Gauteng and Free State provinces between September 2012 and September

CAST-NET

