2 OBJECTIVES

2.1 Study Objectives

We seek to evaluate how best to optimize implementation of reflex laboratory CrAg screening in real-world facilities across South Africa in order to improve the HIV care continuum and thus maximize the survival of persons living with AIDS.

Primary objective (Years 1 and 2): To implement enhanced surveillance at selected sites to determine the outcomes (overall and for pre-specified subgroups) of a national reflex laboratory CRAG screening and pre-emptive treatment programme in South Africa.

Primary objective (Years 2-5): To implement and test programmatic interventions to improve 6-month cryptococcal-free survival.

Examples may include:

- a) Enhanced diagnostics to customize or differentiate patient care
 - a. Using CRAG titre results (e.g. ≥160 titre) to guide when to recommend to perform lumbar puncture (LPs) to detect subclinical meningitis
 - b. Using CRAG titre results to guide recommendations for enhanced antifungal therapy
 - c. Validate CRAG diagnostics
- b) Healthcare provider training
 - a. Training in an online/digital creative format
 - b. Refresher training: Determine frequency of refresher training associated with adherence to national protocols and patient outcome
 - c. Patient education
- c) Enhanced laboratory services: Determine benefit of enhanced methods to deliver CD4 and CRAG results to requestors
 - a. Using SMS to healthcare providers (or SMS alerts to patients to return to the facility for urgent results)
 - b. Contacting patients directly with CRAG results with provision of simple instructions for required next steps
 - c. Confidential "results for action reports" to district and facility managers (i.e. line lists of CRAG+ patients and patients with a CD4<100 but no CRAG test result)

Secondary Objectives:

2. Evaluate cost-effectiveness of a real-world CRAG screening and pre-emptive treatment programme on the ground in South Africa.

3. Evaluate risk factors for treatment failure.

Exploratory Objectives:

- 4. Measure the impact of same day test and treatment on timing of ART initiation among CRAG+ and CRAG negative individuals.
- 5. Describe the prevalence of opportunistic infections in CRAG+ and CRAG negative individuals

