2.2.2 Secondary Outcome Measures

- 1. 6-month retention in care
- 2. Operational challenges of implementation including:
 - a. Time from CD4 testing, CRAG testing, antifungal therapy, and ART initiation among those with a CRAG+ result
 - b. Proportion of CD4/ CRAG results that are received, acknowledged and acted upon by a health practitioner
 - c. Proportion of patients with advanced disease receiving TB screening
 - d. Proportion of CRAG+ persons who develop symptomatic cryptococcal meningitis
 - e. Completion of lumbar puncture when clinically indicated
 - f. Availability of lumbar puncture and appropriate antifungal therapy in routine clinical practice
 - g. Loss to follow-up after CRAG screening and/or during antifungal therapy
 - Proportion of clinicians and staff trained on the CRAG screening algorithm and CRAG lateral flow assay (LFA) (the latter only for facilities that are distant from a laboratory)
 - i. Adherence to CRAG screening and pre-emptive treatment guidelines by healthcare practitioners
- 3. Costs of CRAG+ treatment programs, Incremental cost-effectiveness ratio (ICER)

2.2.3 Exploratory outcome measures:

- 1. Time to ART initiation in test and treat programs amongst HIV-infected persons with advanced disease.
- 2. Prevalence of opportunistic infections in HIV-infected persons with advanced disease

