4.2 Subject Exclusion Criteria

• Age <18 years

Rationale for Criteria:

This project will generate an epidemiological dataset and will then explore the primary endpoint for pre-specified subgroups, along with operational challenges amongst specific subgroups.

STUDY EVALUATIONS 5

We will collect 3 types of data: patient-level, clinic-level, and laboratory-level.

Patient-level data

Chart review will occur approximately 3 times over a 6 month period, with the goal of capturing the patient-level information on CRAG+ persons. Timing of these chart reviews will be variable.

The chart abstractor will ensure that the subject has a positive CRAG result. If so, additional clinical information will be extracted from the chart (see below).

Informed consent will not be obtained for this study, as we are retrospectively collecting demographics and outcomes for CRAG+ and CRAG- patients in routine care. Please see Informed Consent section below.

Baseline demographic information will be obtained, including age, sex, date of birth, location, distance from clinic. Thereafter information about CRAG screening will be obtained. Namely, whether CRAG results were returned to the medical chart and how the healthcare provider acted on these results. If symptomatic, were they offered an LP? If asymptomatic were they prescribed fluconazole? What were the doses and dates of fluconazole therapy, and were there any side effects. Timing of initiation of ART and active treatment for TB will be obtained from the chart. Survival status, along with the date that the patient was last known to be alive will also be collected.

	ecieu
Evaluations	Monitoring Visit
CRAG+, titre	х
CD4 count	Х
Baseline demographic data	Х
If symptomatic, receipt of LP	х
If asymptomatic, receipt of fluconazole	х

Patient-level	data	to be	collected

Evaluations	Monitoring Visit
Completion of fluconazole	Х
Initiation of ART (timing)	Х
Concurrently on TB treatment	Х
Incidence of cryptococcal Meningitis	Х
6-month retention in care	х
6-month vital status	Х

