9.2 Ethics Committee Review

We are retrospectively monitoring an ongoing national screening programme that is considered standard of care in South Africa. Data collection will only be performed retrospectively, thus informed consent will not be obtained for this study.

If further interventions that are beyond the standard of care are pursued, an amendment will be made to this protocol, and further review will be pursued with the local ethics committees.

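### Opportunistic-infection prevalence by CRAG status, taken from routine laboratory records, will depend on who was tested

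*Protocol*

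**What the plan says.** Section 2.1 lists as exploratory objective 5: "Describe the prevalence of opportunistic infections in CRAG+ and CRAG negative individuals". Section 3.1 repeats the aim ("we will describe the prevalence of opportunistic infections amongst CRAG+ and CRAG negative persons") and names the source: "These data will be obtained from laboratory records: toxoplasmosis serology, MTB/Rif GeneXpert results, beta d glucan results, urine LAM, etc".

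Other sections show how those records arise:

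- Section 9.2: "Data collection will only be performed retrospectively, thus informed consent will not be obtained for this study".
- Section 5, patient-level data: the study is "collecting demographics and outcomes for CRAG+ and CRAG- patients in routine care".
- Section 2.2.2 makes TB screening an outcome to be measured: "Proportion of patients with advanced disease receiving TB screening". Section 3, Intervention 3, considers text-message reminders to providers to do that screening.
- Section 1.1, on the NHLS data warehouse: "Other routine laboratory results are also available through the CDW, which can potentially be used as a proxy for retention-in-care".
- Section 1.1, on the cascade of care, says that a CRAG+ result should be handled as a critical value, with the provider notified, the patient recalled urgently and symptoms assessed. It lists no such recall for a negative result.
- Section 9.4 allows batched testing of specimens for CRAG titre, CRP and possible risk factors for treatment failure. It names no opportunistic-infection test.

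**The concern.** A prevalence needs the infection status of everyone in the group, or of a sample whose selection is unrelated to infection. Records from routine care give status only for persons for whom a test was requested. The phrase *clinically ordered* is not in the protocol, but it follows from retrospective collection in routine care with no testing required by the study.

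The objective sets two groups side by side. If the chance of being tested, or how far testing is steered by suspected infection, differs between CRAG+ and CRAG-negative persons, the two figures can differ when disease does not, or agree when disease differs. A reader of the results would have no means of telling which.

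**Working it through.** The protocol gives no sample size, prevalence or testing rate for this objective, so there is no figure to reproduce. Every rate below is an assumption chosen to show the mechanism. Test results are taken as correct.

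**Notation, within one CRAG group.** *p* = true prevalence; *d* and *u* = probability of being tested with and without the infection.

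- Fraction tested: *t* = *pd* + (1 − *p*)*u*
- Positives over all persons: *A* = *pd*
- Positives among tested: *B* = *pd* / *t*
- Bounds on *p* with the untested counted as all negative or all positive: *pd* to *pd* + (1 − *t*)

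If testing is unrelated to infection (*d* = *u* = *t*), then *A* = *pt* and *B* = *p*. The all-persons figure shrinks by the fraction tested, and the tested-only figure is right. If testing depends on infection, *B* is no longer *p*.

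**True prevalence 20% in both groups:**

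| Assumed testing | Fraction tested, CRAG+ / CRAG− | All persons | Tested only |
|---|---|---|---|
| 1. Unrelated to infection, 60% / 30% | 60% / 30% | 12% / 6%, ratio 2.0 | 20% / 20%, ratio 1.0 |
| 2. CRAG+ 80% for all; CRAG− 80% if infected, 30% if not | 80% / 40% | 16% / 16%, ratio 1.0 | 20% / 40%, ratio 0.5 |
| 3. CRAG+ 80% if infected, 40% if not; CRAG− 40% and 20% | 48% / 24% | 16% / 8%, ratio 2.0 | 33% / 33%, ratio 1.0 |

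Row 1: 0.20 × 0.60 = 0.12 and 0.20 × 0.30 = 0.06.

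Row 2: CRAG+ 0.16 / (0.16 + 0.64) = 0.20; CRAG− 0.16 / (0.16 + 0.24) = 0.40.

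Row 3: 0.16 / (0.16 + 0.32) = 0.33 and 0.08 / (0.08 + 0.16) = 0.33.

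**Range.** When testing is unrelated to infection, the all-persons ratio equals the ratio of testing rates at any prevalence: 50% / 40% gives 1.25, 60% / 40% gives 1.5 and 90% / 30% gives 3.0. Under the row 2 testing pattern the tested-only ratio is 0.44 at 10% prevalence (0.10 / 0.229) and 0.56 at 30% (0.30 / 0.533).

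**Bounds.** Row 1: CRAG+ 12% to 0.12 + 0.40 = 52%; CRAG− 6% to 0.06 + 0.70 = 76%. Row 2: CRAG+ 16% to 0.16 + 0.20 = 36%; CRAG− 16% to 0.16 + 0.60 = 76%. All four contain the true 20%, and their width shows how little is known when few are tested.

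The all-persons ratio misleads in row 1 and the tested-only ratio in row 2. In row 3 the tested-only ratio is right but both levels are too high. Choosing a denominator does not by itself solve the problem.

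**The case against.** **This is detail for a statistical analysis plan.** Denominator, time window and table layout can be left to a plan that is not at hand, and their absence is no finding. That is right for those details. What stands is that the protocol itself fixes both the quantity (prevalence) and a source that cannot deliver it without complete testing, or testing unrelated to infection.

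**The objective is only descriptive.** No test, ratio or causal contrast is planned. That stands and limits the weight of the point.

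**TB is partly covered.** The number receiving TB screening is collected by clinic (Section 5.1), and active TB treatment is abstracted from charts (Section 5). Both help, but neither is named as the source for this objective. The protocol does not say that screening will be shown by CRAG status, and nothing comparable is described for the other infections.

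**Testing may not differ much by CRAG status.** A reader might infer that CRAG+ persons are in fact recalled and tested more, so that their prevalence will look too high. The documents do not support that. Recall is listed in Section 1.1 among steps still to be optimised, and the same section reports 63% of CRAG+ persons treated with fluconazole, 48% loss to follow-up in a pilot, and poor linkage to laboratory results. TB screening is framed for advanced disease irrespective of CRAG status. A difference in testing is possible; its size and sign are open.

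**Matching might help.** The 2:1 matching on clinic, CD4 count and CD4 date is stated for the study of ART timing. Even if it applied here, it would not equalise testing after the CRAG result.

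**The listed tests may not diagnose active disease.** A reader might infer that serology or beta-d-glucan is a marker and not a diagnosis. The protocol says nothing on this, so the point does not rest on it.

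**Conclusion.** The concern holds in limited form. The stated quantity and the stated source do not fit together: figures built from routine laboratory records depend on who was tested, whichever denominator is used. A reader might take the doubling in the first illustration as the expected bias. It is not: it arises only with all persons as denominator and an assumed 60% against 30% tested, and it vanishes among those tested if testing is unrelated to infection. Across the assumptions shown, spurious ratios run from 0.44 to 3.0, in both directions. The conclusion rests on the absence of study-required testing and on TB screening being measured and not assumed complete. It touches one exploratory, descriptive objective and leaves the primary endpoint untouched.

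**What to change.** For each infection and each CRAG status, report the number tested, the proportion tested and the positivity among those tested, within a fixed window around the index CD4 date. Label the result *positivity among tested* or *laboratory-detected infection*, not prevalence. Add the bounds that count all untested persons as negative and then as positive. Interpret a difference by CRAG status only beside the tested fractions. For TB, also show the chart-abstracted treatment data where they are collected.

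This makes the bias visible but does not remove it, since positivity among tested is distorted when testing depends on infection. No new patient contact is needed. The extract must keep negative as well as positive results, which the protocol does not say it does, and the objective becomes less ambitious.
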